8.3. Deaths and Serious Adverse Events

In the event that a subject has withdrawn consent, no data after the withdrawal of consent date from this subject including death is supposed to appear in the database, which should be part of the data cleaning process. All deaths will be summarised based on the number and percentage of subjects. This summary will classify subjects by time of death relative to the last dose of medication (>30 days or ≤30 days) and primary cause of death (disease under study, SAE related to study treatment, or other). A supportive listing will be generated to provide subject-specific details on subjects who died.

All SAEs will be tabulated based on the number and percentage of subjects who experienced the event. Separate summaries will also be provided for study treatment-related SAEs. The summary tables will be displayed in descending order of total incidence by SOC and PT.

A study treatment-related SAE is defined as an SAE for which the investigator classifies the relationship to study treatment as “Yes”. A worst-case scenario approach will be taken to handle missing data, i.e. the summary table will include events with the relationship to study treatment as ‘Yes’ or missing.

SAEs are included in the listing of all adverse events. Separate supportive listings with subject-level details will be generated for

- Fatal SAEs
- Non-Fatal SAEs.

AEs of maximum grade of 3 or higher will be summarized separately by SOC and PT.

8.4. Adverse Events Leading to Discontinuation of Study Treatment and/or Withdrawal from the Study and Other Significant Adverse Events

The following categories of AEs will be summarized separately in descending order of total incidence by SOC and PT and separate supportive listings will be generated with subject level details for those subjects:

- AEs Leading to Permanent Discontinuation of Study Treatment or Withdrawal from Study
- AEs Leading to Discontinuation of Study Treatment
- AEs Leading to Dose Interruptions or Delays
- AEs Leadings to Dose Reductions

8.5. Pregnancies

While pregnancy itself is not considered to be an AE or SAE, any pregnancy complication or elective termination of a pregnancy for medical reasons will be recorded as an AE or SAE as described in the protocol. If subjects and subjects' partner become pregnant while on the study, the information will be included in the narratives and no separate table or listing will be produced.

8.6. Clinical Laboratory Analyses

Laboratory evaluations including the analyses of Chemistry laboratory tests, Hematology laboratory tests, Urinalysis, and liver function tests will be based on GSK Core Data Standards. The details of the planned displays are in [Appendix 12: List of Data Displays](#).

Summary of change from baseline by scheduled visits using mean, median, standard deviation, minimum and maximum will be provided.

Summaries of worst case grade increase from baseline grade will be provided for all the lab tests that are gradable by CTCAE v4.0. These summaries will display the number and percentage of subjects with a maximum post-baseline grade increasing from their baseline grade. Any increase in grade from baseline will be summarized along with any increase to a maximum grade of 3 and any increase to a maximum grade of 4. Missing baseline grade will be assumed as grade 0. For laboratory tests that are graded for both low and high values, summaries will be done separately and labelled by direction, e.g., sodium will be summarized as hyponatremia and hypernatremia.

For lab tests that are not gradable by CTCAE v4.0, summaries of worst case changes from baseline with respect to normal range will be generated. Decreases to low, changes to normal or no changes from baseline, and increases to high will be summarized for the worst case post-baseline. If a subject has a decrease to low and an increase to high during the same time interval, then the subject is counted in both the "Decrease to Low" categories and the "Increase to High" categories.

Separate summary tables for hematology, and chemistry laboratory tests will be produced. Liver function laboratory tests will be included with chemical chemistry.

A supporting listing of laboratory data for subjects with abnormalities of potential clinical concern will be provided. A separate listing of laboratory data with character values will also be provided. For lab test values that can be graded, values of grade 1 or above are defined as values of potential clinical concern. For lab test values that can not be graded, values out of the normal range are defined as values of potential clinical concern.

Detailed derivation of baseline assessment is specified in Section 5.2.

Unless otherwise specified, the denominator in percentage calculation at each scheduled visit will be based on the number of subjects with non-missing value at each particular visit.

8.6.1. Analyses of Liver Function Tests

Summaries of hepatobiliary laboratory events including possible Hy's law cases will be provided in addition to what has been described above.

A plot of maximum total bilirubin versus maximum ALT will be generated. Plots of maximum AST versus maximum LDH and maximum AST versus maximum Creatinine Kinase will be generated.

A Summary of Liver Monitoring/Stopping Event Reporting will be provided. The medical conditions data for subjects with liver stopping events will be listed. The substance use data for subjects with liver stopping events will be listed.

8.7. Other Safety Analyses

The analyses of non-laboratory safety test results including ECGs and vital signs will be based on GSK Core Data Standards, unless otherwise specified. The details of the planned displays are presented in [Appendix 12: List of Data Displays](#).

Unless otherwise specified, the denominator in percentage calculation at each scheduled visit will be based on the number of subjects with non-missing value at each particular visit.

Performance Status

ECOG performance status will be summarized at baseline and each post-baseline scheduled visit. Summaries will use frequency and percentage of subjects at each planned assessment time. A summary of change from baseline by scheduled visits will be performed, as well as the worst case post-baseline and the best case post-baseline changes during the study (improved, no change, deteriorated).

A supporting listing will also be provided.

EKG

A summary of the number and percentage of subjects who had normal and abnormal (clinically significant and not clinically significant) ECG findings will be displayed by scheduled visits as well as for the worst case post-baseline.

The QTc values based on Fridericia formula will be rounded to the integer and the values will be categorized into the following ranges: Grade 0 (<450), Grade 1 (450-480), Grade 2 (481-500), and Grade 3 (\geq 501). Summaries of grade increase will be provided. These summaries will display the number and percentage of subjects with any grade increase, increase to grade 2 and increase to grade 3 in the worst case post-baseline only.

The changes in QTc values will be categorized into the clinical concern ranges which are specific to changes in QTc: 31-60 and >60 msec. A summary of change in QTc value will display the number and percentage of subjects with a change within each range in the worst case post-baseline only. Subjects with missing baseline values will be excluded from this summary.

A listing of QTc values of potential clinical importance will be provided

The summaries and listing of QTc will use the collected values based on Fridericia formula.

A figure plotting the baseline QTc and the worst-case post-baseline values will be produced. The figure will have reference lines at 480 and 500 msec for both the ordinate and the abscissa axes. There will be diagonal reference lines at equality (i.e. a 45 degree line), at equality plus 30 msec, and at equality plus 60 msec.

LVEF

Absolute change from baseline in LVEF will be summarized in the worst case post-baseline only. Only the post-baseline assessments that used the same method (ECHO or MUGA) as the baseline assessments will be used to derive the change from baseline. The change from baseline will be categorized as follows:

- No change or any increase
- Any decrease
- >0-<10 decrease
- 10-19 decrease
- \geq 20 decrease
- \geq 10 decrease and \geq LLN
- \geq 10 decrease and < LLN
- \geq 20 decrease and \geq LLN
- \geq 20 decrease and < LLN

LVEF results will also be listed with subject level details including absolute change from baseline.

Ocular Exams

For best corrected visual acuity (BCVA), if data is available, summary statistics for the logMAR score at baseline, end of study treatment and last follow-up exam will be displayed separately by eye using mean, median, standard deviation, minimum and maximum. Changes of logMAR score from baseline to end of treatment visit, last follow-up exam and maximum (worst) change from baseline will be summarized based on the following categories: no change/improved vision: a change from baseline <0.12 ; a possible worsened vision: a change from baseline ≥ 0.12 to <0.3 ; a definite worsened vision: a change from baseline ≥ 0.3 . Subjects with character values of visual acuity exam results will not be included in this summary.

Number and percentage of subjects who experienced corneal clinical signs will be summarized. Among subjects who experienced corneal clinical signs, number and percentage of subjects with/without reported corneal events will be provided. If data is available, the summary will also be provided at end of study treatment visit and last follow-up exam. Visual acuity/ abnormal corneal exam results (eye level) at each visit, and incidence of corneal clinical signs and reported corneal events (subject level) during the study will be listed. The findings considered 'corneal clinical signs' were identified from the pre-defined list of choices in the eCRF.

Listing of abnormal conjunctival exam results, listing of abnormal slit lamp Lens and slit lamp anterior chamber exam results and listing of indirect fundoscopic exam and intra-ocular pressure results will be provided separately.

Constitutional Symptoms (or B-Symptoms)

A summary of the number and percentage of subjects with any constitutional symptom /B-symptom will be displayed by scheduled visits. A summary of improvement, i.e. number of subjects who had no symptoms at each post-baseline scheduled visit and had at least one at baseline, will also be provided.

A supporting listing will be provided.

Organ Examination

The number and percentage of subjects with normal or enlarged organs based on liver and spleen examination by palpation/CT scan will be summarized by scheduled visits.

A supporting listing will also be provided.

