A separate summary will be provided for study treatment-related AEs. A study treatment-related AE is defined as an AE for which the investigator classifies the relationship to study treatment as “Yes”. A worst-case scenario approach will be taken to handle missing relatedness data, i.e. the summary table will include events with the relationship to study

treatment as 'Yes' or missing. The summary table will be displayed in descending order of total incidence by SOC and PT and Maximum Grade.

All AEs will be listed. Additionally, a listing of subject IDs for each individual AE will be produced.

A listing of adverse events recorded as dose-limiting toxicities will be provided. Additionally, a summary of the number of patients experiencing DLT's in each cohort will be provided.

The summary of adverse event by SOC and PT and maximum grade, and AE by PT will also be produced for the following subgroups:

Prior anti-cancer therapy of interest:

- With prior Daratumumab Treatment and Refractory to Both Immunomodulators and Proteasome Inhibitors
- Without prior Daratumumab Treatment
- Refractory to Both Immunomodulators and Proteasome Inhibitors

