16.6.3. Efficacy

Laboratory Parameters
Serum M-protein, Urine M-protein, Serum FLC

 • If a laboratory value which is expected to have a numeric value for summary purposes, has a non-detectable level reported in the database, where the numeric value is missing, but typically a character value starting with '<x' or '>x' (or indicated as less than x or greater than x in the comment field) is present, the number of significant digits in the observed values will be used to determine how much to add or subtract in order to impute the corresponding numeric value. 
 ○ Example 1: 2 Significant Digits = '< x' becomes x - 0.01 ○ Example 2: 1 Significant Digit = '> x' becomes x + 0.1 ○ Example 3: 0 Significant Digits = '< x' becomes x - 1

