16.7.2. Handling of Missing Data

Element	Reporting Detail
General	
 • Missing data occurs when any requested data is not provided, leading to blank fields on the collection instrument: 
 ○ These data will be indicated by the use of a blank in subject listing displays. Unless all data for a specific visit are missing in which case the data is excluded from the table. ○ Answers such as “Not applicable” and “Not evaluable” are not considered to be missing data and should be displayed as such.
Outliers	
 • Any participants excluded from the summaries and/or statistical analyses will be documented along with the reason for exclusion in the clinical study report.
Responder Analysis	
 • For endpoints which determine the percentage of responders, subjects with unknown/not evaluable or missing best overall response will be assumed to be non-responders, and will be included in the denominator when calculating the percentages.
Time to Event	
 • Because study treatment is dependent on the study endpoints (e.g., progression, i.e. not a fixed treatment duration), the length of treatment for each subject will depend on the efficacy and toxicity of the treatment, so the duration of treatment will vary across subjects. Similarly the duration of follow up will also vary. All available time-to-event data will be analyzed using suitable statistical methods; subjects with shorter treatment and follow-up due to the natural history of their disease or medical necessities of the treatment of their disease will not be considered to have missing time-to-event data.

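### The by-eye logMAR change summary drops whole subjects who have any character acuity value, losing usable results and possibly some definite losses of vision

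*SAP*

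**What the plan says.** Under Ocular Exams, section 8.7 says that "summary statistics for the logMAR score at baseline, end of study treatment and last follow-up exam will be displayed separately by eye". Change in logMAR from baseline is then put into three classes: below 0.12 (unchanged or better), 0.12 to below 0.3 (possible worsening) and 0.3 or more (definite worsening). This is done for end of treatment, last follow-up and the worst change. The paragraph closes with "Subjects with character values of visual acuity exam results will not be included in this summary".

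That sentence is not limited to the affected eye or visit. The SAP does not define the character values, convert them to numbers, assign them to a class or ask for a count of those excluded. The tables are 3.0500 to 3.0503 in section 16.12.8.

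Two other provisions bear on it. The opening of section 8.7 sets a default: percentages at a scheduled visit use the subjects with a non-missing value at that visit, unless otherwise specified. Section 16.7.2 says "Missing data occurs when any requested data is not provided, leading to blank fields on the collection instrument", so a text entry is a recorded answer and not missing data. The same section requires any participant left out of a summary to be documented, with the reason, in the study report.

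**The concern.** There are two separate problems.

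The first needs no assumption about the text values. The table is by eye and the exclusion is by subject. One unusable result therefore removes usable ones, and the section's own visit-level denominator is replaced by a much broader rule.

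The second is conditional. An acuity result recorded without a logMAR number may mean that the eye could not read the chart. If so, a subject leaves both numerator and denominator because of the outcome being counted.

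Changes in clinical signs are part of the primary endpoint (section 2.2), and corneal events are adverse events of interest (section 8.2). Tables 3.0500 to 3.0503 are the only listed displays that categorise acuity change. The end-of-study table list (section 4.1.4) contains none, so no later table would correct the figure.

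**Working it through.** The SAP states no rate or count for this summary, so there is no figure to reproduce.

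**Unit of exclusion.** Count what the table shows for a subject with follow-up exams, taking the change classes as by eye. The SAP is explicit on this for the descriptive statistics and only implies it for the classes.

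- logMAR values: 3 time points × 2 eyes = 6.
- Change classes: end of treatment, last follow-up and worst × 2 eyes = 6.
- Total: 12 entries.

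Suppose one eye has an uninformative text entry at end of treatment. The entries that cannot be filled are that eye's end-of-treatment value and its change class, 2 of 12. The worst change can still be taken from the other numeric visits. The rule as written removes all 12, so 12 − 2 = 10 usable entries are lost. If the entry falls at a mid-treatment visit, all 12 can still be filled and all 12 are lost. For a subject without follow-up exams the total is (2 + 2) × 2 = 8 entries, and the end-of-treatment case loses 8 − 2 = 6 usable ones.

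**Effect on the definite-worsening percentage.** Let n be the subjects in the cohort, d those with definite worsening in one eye, k those excluded for a text value, and j the number of those k who are definite losses.

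- All kept: d/n.
- Rule as written: (d − j)/(n − k).
- The reported figure is too low when (d − j)/(n − k) < d/n, which reduces to j/k > d/n. It is too high when j/k < d/n.

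The direction therefore depends on whether definite losses are more common among the excluded than in the whole cohort, and the SAP gives no information on that.

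Inputs: n = 40, the maximum for the Part 2 myeloma cohort (section 2.3). The values of d and k are assumed.

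| d/n | k | all k are losses: (d − k)/(n − k) | none are: d/(n − k) |
|---|---|---|---|
| 4/40 = 10% | 1 | 3/39 = 7.7% | 4/39 = 10.3% |
| | 2 | 2/38 = 5.3% | 4/38 = 10.5% |
| | 4 | 0/36 = 0% | 4/36 = 11.1% |
| 8/40 = 20% | 1 | 7/39 = 17.9% | 8/39 = 20.5% |
| | 2 | 6/38 = 15.8% | 8/38 = 21.1% |
| | 4 | 4/36 = 11.1% | 8/36 = 22.2% |
| 12/40 = 30% | 1 | 11/39 = 28.2% | 12/39 = 30.8% |
| | 2 | 10/38 = 26.3% | 12/38 = 31.6% |
| | 4 | 8/36 = 22.2% | 12/36 = 33.3% |

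The k = 4 cells in the all-loss column are extreme. They need every loss (4 of 4), half (4 of 8) or a third (4 of 12) to carry a text value.

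**Comparison within the SAP.** The LVEF paragraph of section 8.7 drops assessments made by a different method from baseline and keeps the subject. The QTc change summary excludes a subject only where no change can be computed: "Subjects with missing baseline values will be excluded from this summary". The acuity rule is broader than both.

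**The case against.** A reader might infer that the rule hides the worst visual outcomes and understates harm. The documents do not support that. The character values are undefined, and the text answers that section 16.7.2 names as not missing are not applicable and not evaluable, neither of which carries acuity information. If the entries are of that kind, the percentage moves slightly up.

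A reader might also count every scheduled exam, up to 17 or 34 eye results on treatment, and say that one text value discards 33 others. The table does not tabulate those results. It shows baseline, end of treatment, last follow-up and worst change.

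Nor is it fair to say that the SAP always retains such cases elsewhere. Section 16.6.3 gives a number to results reported as below or above a limit (the significant digits "will be used to determine how much to add or subtract in order to impute the corresponding numeric value"), but those results carry a numeric bound and acuity text need not. The rules "A worst-case scenario approach will be taken to handle missing relatedness data" (section 8.1) and "Missing baseline grade will be assumed as grade 0" (section 8.6) concern missing data, and the non-responder rule in section 16.7.2 concerns efficacy. Section 8.6 places laboratory character results in a separate listing, which resembles the treatment of acuity.

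Other outputs limit the harm. Acuity is listed by eye and visit (listing 30.0260). Corneal events are tabulated by maximum grade, and corneal signs are summarised at end of treatment and last follow-up. Exclusions must be documented. The acuity classes are descriptive, with no test or decision attached.

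All of this stands as a limit on severity. None of it corrects the subject-level exclusion or the tabulated percentage.

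**Conclusion.** The point holds in limited form. The unit mismatch is certain on the wording: usable numeric results for the fellow eye and other visits are discarded. In the example with follow-up exams, 10 of the subject's 12 table entries are lost needlessly.

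The loss of definite worsening from the count is possible and not shown. It requires that some text values mean off-chart vision, and a downward bias requires such losses to be more frequent among the excluded than in the cohort. With 8 of 40 assumed, the reported figure could lie anywhere from 11.1% to 22.2% for one to four exclusions, against 20% with everyone kept. These figures illustrate sensitivity and do not estimate a bias. The change is a cheap improvement to a stated rule.

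**What to change.** Replace the closing sentence of the acuity paragraph in section 8.7 with a rule per eye and visit:

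- Before database freeze, review the character values and map each one.
- Count a post-baseline off-chart result after a numeric baseline as definite worsening for that eye and visit, including in the worst-change row.
- Set text with no acuity information to missing for that eye and visit only.
- Show the number of results handled in each way.
- State that the change classes are by eye.

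Apply this to tables 3.0500 to 3.0502, and to 3.0503 only if it is produced, since the end-of-study list omits it and section 1.1 of that amendment says that most lymphoma displays will be listings.

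The cost is a small mapping task on text already in the database and a re-run of those tables. The one drawback is that the change classes will include some subjects who are absent from the mean and median logMAR rows. A footnote can say so.

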30.0340	All Treated	SAFE_L2	Listing of Abnormal Slit Lamp Anterior Chamber and Slit Lamp Lens Exam Results (All Treated MM)	Report for sub-population: All Treated MM. Please include screening results and any post-baseline abnormal results for each patient. Include: Centre ID/ Subj., Age(y)/ Sex/ Race, Reported Corneal Events (Y/N), Cycle/Visit, Time Since 1st Dose/ Time Since last Dose, Eye, Exam Test, Result	EOS SAC
30.0341	All Treated	SAFE_L2	Listing of Abnormal Slit Lamp Anterior Chamber and Slit Lamp Lens Exam Results (Part 2 NHL)	Report for sub-population: Part 2 NHL. Please include screening results and any post-baseline abnormal results for each patient. Include: Centre ID/ Subj., Age(y)/ Sex/ Race, Reported Corneal Events (Y/N), Cycle/Visit, Time Since 1st Dose/ Time Since last Dose, Eye, Exam Test, Result	EOS SAC
30.0350	All Treated	SAFE_L2	Listing of Indirect Fundoscopic Exam and Intraocular Pressure Results (All Treated MM)	Report for sub-population: All Treated MM. Include: Centre ID/ Subj., Age(y)/ Sex/ Race,	EOS SAC

Non-ICH: Listings					
No.	Population	IDSL / Example Shell	Title	Programming Notes	Deliverable [Priority]
				Reported Corneal Events (Y/N), Cycle/Visit, Time Since 1st Dose/ Time Since last Dose, Eye, Exam Test, Result	
30.0351	All Treated	SAFE_L2	Listing of Indirect Fundoscopic Exam and Intraocular Pressure Results (Part 2 NHL)	Report for sub-population: Part 2 NHL. Include: Centre ID/ Subj., Age(y)/ Sex/ Race, Reported Corneal Events (Y/N), Cycle/Visit, Time Since 1st Dose/ Time Since last Dose, Eye, Exam Test, Result	EOS SAC
30.0810	All Treated	SAFE_L2	Listing of Visual Acuity and Abnormal Corneal Exam Results for Subjects with Ocular Exam Results in Follow-up (All Treated MM)		EOS SAC
30.0811	All Treated	SAFE_L2	Listing of Visual Acuity and Abnormal Corneal Exam Results for Subjects with Ocular Exam Results in Follow-up (Part 2 NHL)		EOS SAC
Health Outcomes					
30.0590	All Treated	VS4	Listing of Symptom Impact and HRQoL Item Scores (All Treated MM)	Report for sub-population: All Treated MM. Use the format of VS4, use collected visit dates. List scores for Bone Pain Worst, Bone Pain Average, Fatigue	EOS SAC
30.0591	All Treated	VS4	Listing of Symptom Impact and HRQoL Item Scores (Part 2 NHL)	Report for sub-population: Part 2 NHL. Use the format of VS4, use collected visit dates. List scores for Bone Pain Worst, Bone Pain	EOS SAC

Non-ICH: Listings					

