33. Optional follow-up telephone interview to explore visual symptoms and changes in symptoms and related impacts following treatment discontinuation be performed at least 6 months following the End of Study Treatment visit. This interview would only be for those subjects who experienced corneal symptoms during treatment and consent to participate.
34. End of treatment visit should be performed within 30 days (+7 days) after the last dose or prior to the start of new anti-cancer treatment, whichever is earlier. In cases where more than 30 days (+7 days) have elapsed from the date of the subject's last dose due to dosing delays and a subsequent decision to take the subject off treatment, the end of study treatment visit should be scheduled as soon as possible to allow the final assessments to be performed at the earliest date.

35. Participants with corneal signs or symptoms at the end of study treatment visit should be monitored by ophthalmic exam once a month after the last study dose until deemed clinically stable by an eye care professional complete resolution or for 12 months (whichever comes first). Corneal exams to include BCVA and slit lamp examination (with special focus on cornea). Participants who have completed treatment or the 3 month follow up visit (end of study) will be re-consented for additional ophthalmology follow up.

Abbreviations:

ADA = Antibody Drug Antibody; ALP = alkaline phosphatase; BCVA = best corrected visual acuity; BNP = B-type natriuretic peptide; C1D1 = Cycle 1 Day 1, etc.; cfDNA = Circulating free DNA; CK = creatinine kinase; CRP = C-reactive protein; EM = extramedullary; EOI = End of Infusion; FLC = free light chain; PD = Pharmacodynamics; PK = Pharmacokinetics; QID = 4 times a day; SOI = start of infusion; SPEP = serum protein electrophoresis; UPEP = urine protein electrophoresis

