26. End of treatment visit should be performed within 30 days (+7 days) after the last dose or prior to the start of new anti-cancer treatment, whichever is earlier. In cases where more than 30 days (+7 days) have elapsed from the date of the subject's last dose due to dosing delays and a subsequent decision to take the subject off treatment, the end of study treatment visit should be scheduled as soon as possible to allow the final assessments to be performed at the earliest date.
27. All participants should be followed for survival for 1 year from last dose. Participants with corneal signs or symptoms at the end of study treatment visit should be monitored by ophthalmic exam every month after the last study dose until deemed clinically stable by an eye care professional or for 12 months (whichever comes first). Corneal exams to include BCVA and slit lamp examination (with special focus on cornea).

CONFIDENTIAL

BMA117159

Abbreviations:

ADA = Antibody Drug Antibody; ALP = alkaline phosphatase; BCVA = best corrected visual acuity; BNP = B-type natriuretic peptide; C1D1 = Cycle 1 Day 1, etc.; cfDNA = Circulating free DNA; CK = creatine kinase; CRP = C-reactive protein; EOI = End of Infusion; PD = Pharmacodynamics; PK = Pharmacokinetics; QID = 4 times a day; SOI = start of infusion

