3.0522	All Treated	ESI1	Summary of Characteristics of Corneal Events (All Treated MM)	Report for: All Treated MM, (Summarize: Total). Summary based on both all subjects and subjects with events.	SAC [A]
3.0523	All Treated	ESI1	Summary of Characteristics of Corneal Events (Part 2 NHL)	Report for: Part 2 NHL, (Summarize: only for 3.4 NHL) Summary based on both all subjects and subjects with events.	SAC
3.0180	All Treated	ESI2b	Summary of Onset and Duration of the First Occurrence of Corneal Events (Part 1)	Report for: Part 1, (Summarize: by ascending dose level, Total). Time of onset: 1-21, 22-42, 43-63, >63. Duration till resolution: 1-21, 22-42, >42.	SAC [A]
3.0181	All Treated	ESI2b	Summary of Onset and Duration of the First Occurrence of Corneal Events (Part 2 MM)	Report for: Part 2 MM, (Summarize: only for 3.4 MM) Time of onset: 1-21, 22-42, 43-63, >63. Duration till resolution: 1-21, 22-42, >42.	SAC [A]
3.0182	All Treated	ESI2b	Summary of Onset and Duration of the First Occurrence of Corneal Events (All Treated MM)	Report for: All Treated MM, (Summarize: Total). Time of onset: 1-21, 22-42, 43-63, >63. Duration till	SAC [A]

CONFIDENTIAL

BMA117159

Safety: Tables					
No.	Population	IDSL / Example Shell	Title	Programming Notes	Deliverable [Priority]
				resolution: 1-21, 22-42, >42.	
3.0183	All Treated	ESI2b	Summary of Onset and Duration of the First Occurrence of Corneal Events (Part 2 NHL)	Report for: Part 2 NHL, (Summarize: only for 3.4 NHL) Time of onset: 1-21, 22-42, 43-63, >63. Duration till resolution: 1-21, 22-42, >42.	SAC
3.0150	All Treated	AE3	Summary of Corneal Events Leading to Dose Reduction by Preferred Term (Part 1)	Report for: Part 1, (Summarize: by ascending dose level, Total).	SAC [A]
3.0151	All Treated	AE3	Summary of Corneal Events Leading to Dose Reduction by Preferred Term (Part 2 MM)	Report for: Part 2 MM, (Summarize: only for 3.4 MM)	SAC [A]
3.0152	All Treated	AE3	Summary of Corneal Events Leading to Dose Reduction by Preferred Term (All Treated MM)	Report for: All Treated MM, (Summarize: Total).	SAC [A]
3.0153	All Treated	AE3	Summary of Corneal Events Leading to Dose Reduction by Preferred Term (Part 2 NHL)	Report for: Part 2 NHL, (Summarize: only for 3.4 NHL)	SAC
3.0160	All Treated	AE3	Summary of Corneal Events Leading to Dose Interruptions or Delays by Preferred Term (Part 1)	Report for: Part 1, (Summarize: by ascending dose level, Total).	SAC [A]

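### Primary-analysis ocular tables set last-follow-up results, due only in subjects with corneal signs or symptoms at end of treatment, beside end-of-treatment results for everyone examined, and nothing pairs the two

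*SAP*

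**What the plan says.** - **Time points.** Section 8.7 (Ocular Exams) gives logMAR statistics by eye at baseline, end of study treatment and last follow-up exam. On change it says: "Changes of logMAR score from baseline to end of treatment visit, last follow-up exam and maximum (worst) change from baseline will be summarized". On corneal signs it says: "If data is available, the summary will also be provided at end of study treatment visit and last follow-up exam". The RAP amendment log (Section 1.1 of the November 2018 RAP) records that these time points were added to existing displays, so they share a table.
- **Tables.** Section 16.12.8 lists 3.0491 and 3.0492 (corneal signs) and 3.0501 and 3.0502 (BCVA) for Part 2 MM and All Treated MM, on the All Treated population.
- **Who is examined.** The Part 2 MM schedule (Section 16.2.3.1) puts an ocular exam at the end-of-treatment visit for all subjects. For follow-up, footnote 35 says: "Participants with corneal signs or symptoms at the end of study treatment visit should be monitored by ophthalmic exam once a month". Those who had already finished treatment or the 3-month visit "will be re-consented for additional ophthalmology follow up". The lymphoma schedule (Section 16.2.3.3, footnote 27) has the same condition: "Participants with corneal signs or symptoms at the end of study treatment visit should be monitored by ophthalmic exam every month".
- **Denominator.** The only rule Section 8.7 states is a default that other text may override: "the denominator in percentage calculation at each scheduled visit will be based on the number of subjects with non-missing value at each particular visit".
- **End of study.** The end-of-study safety table list (Section 4.1.4) has no ocular summary table for any cohort. Follow-up eye data appear there in listings such as 30.0810.

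**The concern.** A reader will take the end-of-treatment and last-follow-up entries as before and after. They are not, because the follow-up group was selected for being affected at the first time point. Unaffected subjects count at end of treatment and then drop out, which pushes the follow-up figures up whatever happens to the eyes of those who are followed.

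Counts alone do not settle it. A fall from 16 subjects with signs to 12 could mean that 4 cleared or that 4 had no exam. Missing exams are plausible: follow-up of subjects already off treatment depends on re-consent, and Section 13 says few subjects were still on treatment at the protocol amendment. The Part 1 schedule (Section 16.2.2.1) has no eye exam at off-study follow-up, yet Part 1 is pooled into the All Treated MM tables.

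At stake is the descriptive reading of whether corneal signs and vision recover once dosing stops.

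**Working it through.** The SAP gives no figure for these tables, so there is nothing to reproduce. The check is how far the printed pair can depart from the same-subject pair.

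**Inputs.** N = 40 for Part 2 MM (Section 2.3, up to 40 subjects). The rest are assumptions:
- p = share with signs at end of treatment;
- s = share with symptoms only, who stay free of signs;
- r = share of those with signs who clear;
- everyone with signs or symptoms is followed.

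**Corneal signs, non-missing denominator.**
- End of treatment, as printed: p
- Last follow-up, as printed: p(1 − r)/(p + s)
- End of treatment in the followed subjects: p/(p + s)
- The printed figure rises when p(1 − r)/(p + s) > p, that is, when r < 1 − p − s

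With s = 10% (4 subjects) and r = 25%:

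| p | Printed: end of treatment | Printed: follow-up | Same subjects | Rises if r below |
|---|---|---|---|---|
| 40% | 16/40 = 40% | 12/20 = 60% | 80% to 60% | 50% |
| 50% | 20/40 = 50% | 15/24 = 62.5% | 83.3% to 62.5% | 40% |
| 70% | 28/40 = 70% | 21/32 = 65.6% | 87.5% to 65.6% | 20% |

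The first two rows show false worsening. The third shows a drop of 4.4 points where the true drop is 21.9.

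With r = 50%, the follow-up figures are 8/20 = 40%, 10/24 = 41.7% and 14/32 = 43.8%. None is above its end-of-treatment value, but at p = 40% the table prints 40% twice although half the affected subjects cleared.

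Varying s at r = 25%: s = 0 gives 75% at follow-up in all three rows. s = 20% gives 12/24 = 50%, 15/28 = 53.6% and 21/36 = 58.3%.

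**Corneal signs, All Treated denominator.** At r = 25% the follow-up figures are 12/40 = 30%, 15/40 = 37.5% and 21/40 = 52.5%, each below its end-of-treatment value. With complete follow-up this denominator removes the problem for signs.

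**BCVA change categories (one eye, assumed 20 of 40 followed).** Suppose 6 definite worsenings at end of treatment, all among the followed, of which 2 recover.
- Printed: 6/40 = 15%, then 4/20 = 20%. Same subjects: 6/20 = 30%, then 20%.
- A denominator of 40 does not repair this. Subjects not definitely worse would go from 34/40 = 85% to 16/40 = 40%, a fall that arises because 20 subjects have no exam.

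**BCVA mean (assumed).** Baseline logMAR is 0.10. The change is +0.20 in the 20 followed and 0 in the other 20, with a quarter of it recovered by follow-up.
- End-of-treatment mean, all: 0.10 + 0.5 × 0.20 = 0.20
- Follow-up mean, followed: 0.10 + 0.75 × 0.20 = 0.25
- Same subjects: 0.30, then 0.25

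Vision improved, and the printed means show it worsening. No choice of denominator helps, because unfollowed subjects have no follow-up logMAR value.

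**The case against.** **The plan does make a matched comparison.** BCVA change at last follow-up is measured from each eye's own baseline, so a followed eye still 0.3 or more above baseline is correctly called worse. This stands. What is missing is only the pairing of end of treatment with last follow-up.

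**The sign denominator is not established.** The non-missing rule is worded for scheduled visits, whereas a last follow-up exam is derived per subject. Shells SAFE_T1 and SAFE_T2 are not in the text at hand. This stands for the sign percentages, so that part of the point is conditional. It does not help the BCVA rows.

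**Other displays cover recovery.** Listing 30.0810 shows the followed subjects one by one, Table 3.0181 gives duration of the first corneal event, and profile plots 13.0190 and 13.0191 show Part 2 MM subjects by corneal-event grade. With at most 40 subjects in Part 2 MM, such displays can be read directly. This is real but partial mitigation: none is a pooled, exam-based summary of the same subjects at both times. The general reporting convention (N, n, frequency, %) would show a smaller n, but not why it is smaller.

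**The size is constructed.** This is true. A reader might infer that the tables will show false worsening, but the documents give no rate of signs, symptoms, clearing or missing exams, and the direction turns on r.

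**The end-of-study report.** A reader might also infer that the most mature follow-up data will be presented this way. They will not: the end-of-study list omits the MM ocular tables as well as the NHL ones (3.0493, 3.0503). The issue lies in the primary-analysis tables.

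**Conclusion.** The point holds, at minor severity. As written, the primary-analysis ocular tables for Part 2 MM and All Treated MM place an affected-only group beside all examined subjects, with no result pairing the two time points. The BCVA means and change categories are affected under any denominator. The corneal-sign percentages are affected if the non-missing denominator is the one used.

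Depending on assumed clearing rates, apparent recovery can be understated, hidden or reversed. With 10% symptoms only and a quarter clearing, reversal occurs at 40% and 50% with signs but not at 70%. With half clearing it occurs in none of the three cases. No test, stopping rule or dose decision is touched.

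**What to change.** In Section 8.7, for the last-follow-up rows of Tables 3.0491, 3.0492, 3.0501 and 3.0502:

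1. State the denominator as subjects with a follow-up exam.
2. Beside it, show those same subjects' end-of-treatment result: signs cleared or persisting, and BCVA category and logMAR at both times.
3. Give the number with signs at end of treatment but no follow-up exam.

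Do the same for NHL Tables 3.0493 and 3.0503, or for any ocular summary added at end of study, if produced. Section 8.7 already uses this logic for B-symptoms, where improvement is counted among subjects who had a symptom at baseline.

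The cost is two or three sentences and a few rows. The exam results are already needed for listings 30.0260 and 30.0810, so no new exams or data fields are required. The downside is slightly longer tables.
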